4.1 Number of Patients

Approximately 527 patients are planned to be enrolled in this study across approximately 80 global sites.

4.2 Study Population Characteristics

Evaporative dry eye (EDE)

4.3 Inclusion Criteria

The following are requirements for entry into the study:

[REDACTED]

[REDACTED]

[REDACTED]

[REDACTED]

3. Male, 18 years of age or older, at the screening (day -51) visit

OR

Females, 18 years of age or older, who are naturally menopausal (permanent cessation of menstrual periods for at least 12 consecutive months) or are permanently sterilized (eg, tubal occlusion, hysterectomy, bilateral salpingectomy, and/or bilateral oophorectomy) at the screening (day -51) visit

4. In at least 1 eye, all of the following objective measures of EDE must be present at the standardization (day -21) and baseline (day 1) visits. The same eye must qualify at both visits.

- TBUT \geq 2 seconds and \leq 7 seconds
- Corneal sodium fluorescein staining score \geq 1 and $<$ 4 (Oxford scheme)
- Anesthetized Schirmer's tear test score \geq 10 mm after 5 minutes

5. At the standardization visit (day -21) and baseline (day 1) visits, patients must have:

- Ocular Surface Disease Index[®] (OSDI) score $>$ 12 (0 to 100 scale)

- Overall ocular discomfort score ≥ 1 and < 4 (0 to 4 scale; 0 = none, 4 = very severe)
- Ocular burning score ≥ 1 and < 4 (0 to 4 scale; 0 = none, 4 = very severe)
- Blurred vision score ≥ 1 and < 4 (0 to 4 scale; 0 = none, 4 = very severe)

6. In at least 1 eye, a lower lid margin meibum quality global assessment score ≥ 1 at the standardization (day -21) and baseline (day 1) visits. The same eye must qualify at both visits.
7. In at least 1 eye, the number of lower lid margin expressible meibomian glands must be ≥ 3 at the standardization (day -21) and baseline (day 1) visits. The same eye must qualify at both visits.

[REDACTED]

[REDACTED]

[REDACTED]

[REDACTED]

[REDACTED]

[REDACTED]

[REDACTED]

[REDACTED]

11. Use of an artificial tear product, lid hygiene (ie, warm compress, lid massage, lid scrub), omega-3 supplementation (topical ocular or systemic), or antibiotics (ie, systemic or topical macrolides, tetracyclines, tetracycline derivative drugs [including doxycycline and minocycline]) for the treatment of dry eye disease or meibomian gland disease within 1 year of the standardization (day -21) visit.

4.5 Permissible and Prohibited Medications/Treatments

4.5.1 Permissible Medications/Treatments

The following medications listed in [Table 2](#) are permissible during the interval between the standardization (day -21) visit and the month 12/study exit visits if they have been taken for the minimum number of days listed in Table 2 prior to the standardization (day -21) visit and anticipated continuation on the same dose until at least the month 6 visit:

Table 2 **Permissible Medications That Require Stable Dosing Prior to the Standardization (Day -21) Visit and Anticipated Continuation on the Same Dose Until at Least the Month 6 Visit**

30 Days Before Standardization (day -21) Visit	60 Days Before Standardization Visit	90 Days Before Standardization Visit
Systemic antihistamines	Systemic beta-blocking agents	
Systemic antimuscarinics	Systemic cholinergic agonists	
	Systemic medications used to treat mild to moderate systemic autoimmune disorders ¹	
Diuretics		
Tricyclic antidepressants	Inhaled corticosteroids	
Phenothiazines		
Systemic vitamins and/or systemic supplements containing: omega 3 fatty acids; vitamins A, B, and E; fish oil; biotin or Evening Primrose oil		

Note: any medication previously noted as an exclusion criteria (ie: systemic corticosteroids, calcineurin inhibitors, etc) must follow details noted for prohibited medications.

In addition, the following medications are permissible during the interval between the standardization (day -21) visit and the month 12/study exit visits:

- oral nonsteroidal anti-inflammatory drugs (NSAIDs) or acetaminophen (as needed)
- dermal or nasal corticosteroids (as needed)

The use of any artificial tear product is permissible after the month 6 visit to the month 12/study exit visit.

The use of lid hygiene (ie, warm compress, lid massage, lid scrub) on either eye is permissible after the month 6 visit to the month 12/study exit.

Therapy considered necessary for the patient's welfare may be given at the discretion of the investigator. If the permissibility of a specific medication/treatment is in question, please contact Allergan.

4.5.1.1 Definition of Females of Childbearing Potential and/or Acceptable Contraceptive Methods

For purposes of this study, females will be considered of childbearing potential unless they are naturally postmenopausal or permanently sterilized (ie, tubal occlusion, hysterectomy,

bilateral salpingectomy, and/or bilateral oophorectomy). Natural menopause is defined as the permanent cessation of menstrual periods, determined retrospectively after a woman has experienced 12 months of amenorrhea without any other obvious pathological or physiological cause.

For male patients with a pregnant partner or a female partner of child bearing potential, it is recommended that a barrier method of contraception be employed for the entire duration of the phase 3 study and for 24 hours following the last dose of study treatment.

If a female partner of a male patient becomes pregnant during the study, the investigator will notify Allergan immediately after the pregnancy is confirmed. The investigator will (1) obtain consent from the female partner for pregnancy follow-up and (2) follow the progress of the pregnancy to term. The investigator must document the outcome of the pregnancy and provide a copy of the documentation to Allergan.

4.5.2 Prohibited Medications/Treatments/Procedures

Lid hygiene (ie, warm compress, lid massage, lid scrub) on either eye is prohibited during the interval between the standardization (day -21) visit and month 6 visit.

Contact lens wear in either eye is prohibited during the interval between the standardization (day -21) visit and month 12/study exit visit.

The following facial hair removal procedures applied to chin, cheek, upper lip, and/or brow are prohibited for female patients during the interval prior to each study visit:

- plucking or shaving within 14 days of any study visit
- laser, waxing, sugaring depilatory product, or any other removal process within 30 days of any study visit

The following procedures are prohibited in either eye during the interval between the screening (day -51) visit and month 12/study exit visit:

- punctal cautery
- anterior segment surgery in either eye which could affect corneal sensitivity (eg, cataract surgery, corneal refractive surgery, or any surgery involving a limbal or corneal incision)
- use of any type of punctal plug (eg, nondissolvable or collagen)

- use of any type of scleral lenses
- use of LipiFlow or other lid-heating therapy, meibomian gland probing, or therapeutic gland expression
- use of sealed compartment ocular frames
- upper or lower lid tattooing

The following medications listed in Table 3 are prohibited during the interval between the standardization (day -21) visit and the month 6 visit:

Table 3 Prohibited Medications Within the Period Indicated Prior to the Standardization (Day -21) Visit to Month 6 Visit

At the Standardization Visit	Within 60 Days Before Standardization Visit ^a
All artificial Tears except SAT	Systemic or topical macrolides Topical corticosteroids in the eyes or on the eyelids Oral (systemic) corticosteroids Tetracycline Tetracycline derivatives (eg, doxycycline, minocycline) Retinoids (eg, isotretinoin) Calcineurin inhibitors (eg, RESTASIS, Ikervis) Lifitegrast (Xiidra) Other therapeutic treatments of dry eye

^a all medications listed in table are permissible following the Month 6 visit.

The following medications listed in [Table 4](#) are prohibited during the interval between the standardization (day -21) visit and the month 12/study exit visits:

Table 4

Prohibited Medications Within the Period Indicated Prior to the Standardization (Day -21) Visit and Throughout the Duration of the Study

Within 30 Days Before Standardization (day -21) Visit	Within 60 Days Before Standardization (day -21) Visit	Within 90 Days Before Standardization (day -21) Visit
Topical ocular glaucoma medications	Eyelash growth stimulators (eg, LATISSE)	Androgen or anti-androgen treatment (includes herbal and nutritional supplements)
Topical ocular allergy medications (includes herbal and nutritional supplements)		5-alpha reductase inhibitors (eg, finasteride, dutasteride, bexlosteride, epristeride, izonsteride, lapisteride, turosteride) Spironolactone Inhibitors of steroidogenesis (eg, ketoconazole, abiraterone) Androgen receptor antagonists (eg, flutamide, bicalutamide, nilutamide, galetone, MDV3100) GnRH agonists (eg, deslorelin, nafarelin, leuprolide, buserelin, goserelin, triptorelin, histrelin, deslorelin) Cyproterone acetate Hormone replacement therapy program or other use of estrogen or progesterone (includes herbal and nutritional supplements) Hair growth products

GnRH = gonadotropin-releasing hormone

The decision to administer a prohibited medication/treatment is done with the safety of the study participant as the primary consideration. When possible, Allergan should be notified before the prohibited medication/treatment is administered.

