3.1 Additional Study Design Details

With respect to details described below for each study visit:

1. For patients not participating in the collection of blood samples for pharmacokinetic analysis, study treatment should be administered in the morning at approximately the same time of day during each office visit (\pm 1 hour from the study administration time at baseline [day 1]). At any time, the morning dose time should not exceed 1:00 pm local time.

2. For patients who participate in the collection of blood samples for pharmacokinetic analysis:
 - a. the time of the pre-dose blood sample collection should be scheduled in the morning at approximately the same time of day during each office visit (\pm 1 hour from the pre dose blood sample collection time at the standardization [day -21] visit).
 - b. SAT or study treatment should be administered in the morning at approximately the same time of day during each office visit and within 10 min after the time the pre-dose blood sample collection was performed that day.

Screening Visit (day -51): A patient may enter a screening period if, at the screening visit, applicable medications or treatments are required to be washed out or administered at a stable dose (Section 4.5), prior to commencement of the standardization (day -21) visit. If a screening period is not applicable, the screening and standardization visits may occur on the same day (day -21). For those patients who do enter the screening period, their standardization visit should be scheduled 7 ± 1 days prior to the vehicle run-in (day -14) visit.

Standardization Visit (day -21): Eligible patients will discontinue use of any lid hygiene (ie, warm compress, lid massage, lid scrub) or artificial tears (other than SAT) and will begin administering 1 drop of SAT in each eye twice daily (morning and evening, spaced approximately by 12 hours) for 6 days. For selected patients, blood sample collection for systemic pharmacokinetics will occur prior to in-office administration of SAT and for 12 hours after administration of SAT at the following intervals: 5 ± 1 min; 10 ± 1 min; 30 ± 5 min; 2 hrs ± 15 min; 4 hrs ± 30 min; 6 hrs ± 30 min; 12 hrs ± 30 min. Following the 12 hour sample collection, site staff will remind patient to administer 1 drop of SAT in each eye prior to leaving site.

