6.3 Safety Measures

- adverse events
- BCVA (LogMAR)
- biomicroscopy
- ophthalmoscopy
- intraocular pressure (IOP)
- urine pregnancy test (female patients only)
- PSA (male patients only)
- hematology, serum chemistry, and urinalysis
- vital signs
- male scalp hair evaluation assessed by the investigator using the Norwood Male Pattern Baldness grading scale
- female hair evaluation (upper lip, chin, cheeks, and scalp) assessed by the investigator using the Ferriman and Gallwey scoring (0 to 4) scale for facial hair and the Female Androgenetic Alopecia Ludwig grading scale for the scalp

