7.7 Interim Analyses

There will be no interim analysis.

8. Study Visit Schedule and Procedures

This study will be comprised of a 6-month double-masked treatment phase followed by a 6-month open label treatment extension phase evaluating safety, efficacy, and systemic pharmacokinetics of 0.1% AGN-195263 in patients with EDE. There will be 9 study visits: screening (day -51), standardization (day -21), vehicle run-in (day -14), baseline (randomization, day 1), months 1, 3, 6, 9, and 12/study exit. See [Table 1](#) for a schematic of the schedule of visits and procedures and [Figure 1](#) for schematic diagram of the study design.

[figure not shown]

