8.3.2 Standardization Visit (Day -21 [\pm 1 day])

The following procedures and assessments will be performed during the standardization visit:

- Inclusion/exclusion criteria review (reassessment only for patients whose screening and standardization visits are on separate days)
- Medical and ophthalmic history (reassessment only for patients whose screening and standardization visits are on separate days)
- Concomitant medications (reassessment only for patients whose screening and standardization visits are on separate days). Ensure to query use of:
 - Lid hygiene (warm compress, lid massage, lid scrub)
 - Any artificial tear products
 - Oral or topical macrolides, tetracyclines, tetracycline derivative drugs
- Vital signs (pulse rate, blood pressure)
- Hair evaluation (all patients asked to report any use of hair growth products or hair removal procedures)

- Visual acuity (manifest refraction)
- Biomicroscopy (includes upper and lower lid margin appearance evaluation)

- TBUT
- Sodium fluorescein corneal staining (Oxford scheme)
- Sodium fluorescein conjunctival staining (Oxford scheme)
- At least 10-minute wait
- Schirmer tear test with anesthesia
- Lower lid margin meibomian gland secretion evaluation
- IOP
- Ophthalmoscopy (eyes should be dilated)
- Contact IxRS
- Blood and urine collection sample for hematology, blood chemistry, PSA measurement (males only), and urinalysis
- [REDACTED]
- [REDACTED]
- In-office administration of SAT
- Post-dose blood sample collection for systemic pharmacokinetics (5 minutes \pm 1 minute, 10 minutes \pm 1 minute, 30 minutes \pm 5 minutes, 2 hours \pm 15 minutes, 4 hours \pm 30 minutes, 6 hours \pm 30 minutes and 12 hours \pm 30 minutes) (for selected patients) (To facilitate the 12 hour time course of blood draws for pharmacokinetic analysis at the standardization (day -21) and month 1 visits, sites may “split” the visit, and perform the serial blood draws at a separate visit (the “split visit”). The split visit must occur within 5 days from the scheduled visit.)
- Adverse events
- SAT dispensing

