8.3.3 Vehicle Run-in Visit (Day -14 + [3 days])

Patients will be instructed to not administer morning dose of study treatment the day of a study visit. In addition, patients will be asked to refrain from use of SAT for 1 day prior to each study visit. One day prior to each study visit begins on the morning of the day before the study visit and continues until the end of the study visit.

The following procedures and assessments will be performed during the vehicle run-in visit:

- Concomitant medications. Ensure to query use of:
 - Lid hygiene (ie, warm compress, lid massage, lid scrub)
 - SAT
 - Any artificial tear products other than SAT
 - Oral or topical macrolides, tetracyclines, tetracycline derivative drugs
- Ocular symptoms questions: overall ocular discomfort, blurred vision, ocular burning
- Visual acuity
- Biomicroscopy (includes upper and lower lid margin appearance evaluation)
- TBUT
- Sodium fluorescein corneal staining (Oxford scheme)
- Sodium fluorescein conjunctival staining (Oxford scheme)
- IOP
- Contact IxRS
- In-office administration of study treatment
- Adverse events
- Study treatment dispensing
- SAT dispensing
- Collect unused study treatment

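### The facial hair removal windows run together before day 1, so the baseline score has a longer guaranteed regrowth time than the scores at months 3 to 12

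*Combined protocol and SAP*

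**What the plan says.** Section 4.5.2 lists facial hair removal procedures (chin, cheek, upper lip, brow) that "are prohibited for female patients during the interval prior to each study visit". There are two windows: "plucking or shaving within 14 days of any study visit", and "laser, waxing, sugaring depilatory product, or any other removal process within 30 days of any study visit".

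The opening of Section 8 gives the visits as "screening (day -51), standardization (day -21), vehicle run-in (day -14), baseline (randomization, day 1), months 1, 3, 6, 9, and 12/study exit". Section 3.1 allows screening and standardization to fall on the same day, so a separate day -51 visit is not universal.

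Section 6.3 makes facial hair a safety measure: "female hair evaluation (upper lip, chin, cheeks, and scalp) assessed by the investigator using the Ferriman and Gallwey scoring (0 to 4) scale". The visit lists in Section 8.3 place a hair evaluation at day -21, day 1 and months 1, 3, 6, 9 and 12. The lists for screening (8.3.1) and vehicle run-in (8.3.3) contain none. The day -21 entry also asks about hair removal.

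Section 7.3.4 leaves detailed methods for safety variables to the analysis plan. The available text does not say which pre-treatment hair score is the reference. The hair evaluation attachment (12.1.4) and the wording of exclusion criterion 30 are not in the public text. The amendment summary (12.3) says criterion 30 was added so that removal procedures would not confound the hair evaluations.

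**The concern.** Because the windows attach to every visit, visits that do not score hair lengthen the ban before day 1. Visits at days -21, -14 and 1 are close together; later ones are one to three months apart. The same rule therefore guarantees more regrowth at baseline than at most follow-up visits, which works against its own purpose.

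The direction is not conservative. A baseline taken after longer regrowth tends to be higher, so a later increase can look smaller. Facial hair is a relevant signal here: the protocol measures serum testosterone, DHT and SHBG in selected patients, and it prohibits androgens and hair growth products (Table 4). The safety hypothesis in Section 2.2 spans 12 months, but the vehicle arm ends at month 6. After that, interpretation relies on within-patient change, summarised descriptively.

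**Working it through.** **Inputs.** Windows w = 14 and w = 30 days (Section 4.5.2). Visits as in Section 8. Section 5.6 counts days -14 to -1 as two weeks, so there is no day 0 and day -14 is 14 days before day 1. Assumption: months 1 and 3 fall about 30 and 91 days after day 1. The plan states no regrowth figure to reproduce.

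**Method.** Set day 1 at t = 0, so day -k is t = -k. A visit at v bans removal over [v - w, v]. Minimum regrowth at v is the length of the unbroken run of banned intervals that ends at v.

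**Plucking or shaving (w = 14).**
- Day -21: [-35, -21]. Day -14: [-28, -14]. Day 1: [-14, 0].
- The first two overlap and the third meets the second at -14. The run is [-35, 0], so the day 1 minimum is 35 days.
- A separate day -51 visit bans [-65, -51]. This does not reach -35, so nothing changes.
- Month 1: [16, 30] does not reach 0, so the minimum is 14 days. Later visits are further apart: 14 days.

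**Other methods (w = 30).**
- Day -21: [-51, -21]. Day -14: [-44, -14]. Day 1: [-30, 0]. The run is [-51, 0], so the minimum is 51 days.
- A separate day -51 visit adds [-81, -51], which meets the run at -51: 81 days.
- Month 1: [0, 30] meets day 1, so the minimum is 30 + 51 = 81 days (30 + 81 = 111 with a day -51 visit). If month 1 is more than 30 days after day 1, the run breaks and the minimum is 30.
- Month 3: [61, 91] does not reach 30, so the minimum is 30 days. Months 6 to 12: 30 days.

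| Minimum regrowth (days) | Day -21 | Day 1 | Month 1 | Months 3 to 12 |
|---|---|---|---|---|
| Plucking, shaving | 14 | 35 | 14 | 14 |
| Other methods, no separate screening | 30 | 51 | 81 or 30 | 30 |
| Other methods, separate day -51 visit | 60 | 81 | 111 or 30 | 30 |

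The day 1 excess over months 3 to 12 is 35 - 14 = 21 days for plucking or shaving. For other methods it is 51 - 30 = 21 days, or 81 - 30 = 51 days with a separate screening visit.

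**Sensitivity to visit tolerances.**
- Standardization at ±1 day moves the 35 to between 34 and 36.
- Section 8.3.3 allows 3 days on the run-in visit without explaining the direction. At day -11 the minimum stays at 35. At day -17 the intervals are [-31, -17] and [-14, 0]. A 3-day gap opens, the day 1 minimum falls to 14, and the plucking and shaving mismatch disappears.
- With a separate day -51 visit and standardization at day -20, a one-day gap opens and the 81 becomes 50.
- Month 1 is allowed ±5 days, so its figure under the 30-day rule can be either value in the table.

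**The case against.** **Reference score.** No available passage says that facial hair will be analysed as change from day 1; the analysis plan is not supplied. That stands as a limit. However, the protocol labels day 1 as baseline throughout, and Section 7.3 plans within-treatment tests for ordinal variables in general. Change from day 1 is therefore the natural default unless the plan says otherwise.

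**Minimums, not actual times.** This stands. A woman who plucks just after month 3 and not again has about 91 days of regrowth at month 6, more than the 35-day minimum at baseline. Women who do not remove facial hair are unaffected. A reader might infer that the score is pushed down in every woman who removes hair; the documents do not support that.

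**Effect on the grade.** A reader might take 35/14 = 2.5 or 51/30 = 1.7 as the rise in hair growth that could be hidden. These are ratios of guaranteed times only. Nothing available shows that a 0 to 4 grade tracks regrowth time, or that 2 versus 5 weeks changes it. The claim that androgenic growth is hidden is not shown.

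**Fairness between arms.** Both arms follow the same schedule to month 6, so the randomised comparison is not tilted. Patients who switch from vehicle also have a month 6 score with the same 14- or 30-day minimum as months 9 and 12, which is a like-for-like contrast within the extension. Both points stand. Patients on active drug from day 1 have no such score after the start of treatment.

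**Removal is already queried.** It is asked at day -21, and Section 8.6 asks about concurrent procedures at every visit. The visible text does not require the method and date of last removal at each hair evaluation.

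**Conclusion.** The concern holds as a mismatch in guaranteed regrowth time at the nominal schedule. It is 35 versus 14 days for plucking or shaving at months 1 to 12, and 51 (or 81) versus 30 days for other methods at months 3 to 12. Month 1 under the 30-day rule is an exception, because the windows can still join there and give a longer minimum than day 1.

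For women who remove facial hair close to the last permitted day, change from day 1 can understate an increase. The bias cannot be sized: neither the share of women affected nor the sensitivity of the grade to regrowth time is given. To month 6 the likely cost is sensitivity in both arms, not a tilted comparison. The main exposure is within-patient change in the uncontrolled open-label phase.

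This rests on counting without a day 0, on a run-in visit no more than 14 days before day 1 (plucking and shaving only), and on day 1 being the reference. It is worth correcting because the remedy is cheap and the rule as worded defeats its own aim.

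**What to change.** 1. In Section 4.5.2 and the matching exclusion criterion, tie both windows to visits with a hair evaluation. This removes screening and day -14 as triggers. For plucking or shaving, [-35, -21] and [-14, 0] no longer join, so the minimum is 14 days at day -21, day 1 and months 1 to 12. The 30-day rule is not repaired at day 1: [-51, -21] and [-30, 0] still overlap and give 51 days.
2. In the analysis plan, which Section 7 requires to be approved before the first database lock, report change in female facial hair score from the day -21 evaluation alongside change from day 1. With item 1 in place, the day -21 minimums of 14 and 30 days match months 3 to 12 for all women. Without item 1, women with a separate day -51 visit have up to 60 days at day -21 under the 30-day rule.
3. Record the method and date of last facial hair removal at each hair evaluation. This also makes the remaining month 1 mismatch under the 30-day rule interpretable.

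Cost: one phrase in two places, one sentence in the analysis plan, and one more question at visits that already score hair. No new visit or procedure is needed. The downside is that the day -21 reference lies three weeks before the first randomised dose, which is why change from day 1 should still be shown.
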